Effect of Dialysis Membranes on Inflammatory and Immune Processes in Hemodialysis

Document Date: July 27th, 2018

Study Group

A total of 52 patients older than 18 years and under 65 years of age who have been undergoing hemodialysis for more than 3 months will be included in the study. The planned study time is 6 months. Patients will be randomized in two groups by a computer program. 26 patients were dialyzed by high-flux dialyzer and 26 patients by middle cut-off dialyser for 3 months. At the end of the third month, the dialysers will be crossing in the same groups. The study will end in three months after crossover.

Clinical Evaluation

All patients will be dialyzed according general recommendations with Kt/Vurea higher than 1.4. The dialysate flow rate and pump speed will be maintained at the recommended values according to the patient's vascular access pathway. Serum samples will be taken at 0 (beginning), 4th (90th day) and 7th (180th day) months in the beginning and at the end of dialysis. Blood count, electrolytes, serum albumin and total protein levels will be determined at 0, 4th and 7th months. Urea, creatinine, albumin, free light chain kappa and lambda, β 2 microglobulin, myoglobin levels will be examined; Kt/Vurea values will be calculated. Between the two groups, serum light chain kappa, serum light chain lambda and β 2 microglobulin and myoglobin levels will be compared. The decrease in serum albumin values over time will be compared between the two groups.

Anti-human CD4, anti-human CD4, anti-human CD16, anti-human CD19, and anti-human CD14 / CD45 fluorescent-labeled monoclonal antibodies will be used for immunophenotyping with flow-cytometry. Cell Quest (BD) and FlowJo analysis programs will be used for data analysis to determine cell groups.

Peripheral blood mononuclear cells will be isolated to determine IL-17A (Th17), IL-10 (Treg), IFN gamma and TNF alpha (Th1) and IL-4 (Th2) intracellular cytokine contents. Cells from culture will be staining with anti-CD3, anti-CD4, anti-CD8 and anti-CD25 monoclonal antibody to determine cell surface molecule expressions, and then undergo intracellular cytokine staining.

IL-17A, IL-10, IFN-gamma, TNF-alpha, IL-18, MCP-1, NLRP3, RANTES and calcification, which are specific for T cell subtypes by ELISA and luminex (multi-bead) method and evaluated as a marker of inflammation simultaneously in patient sera. The FGF-23 levels will be determined according to the manufacturer's instructions.

Statistical Analysis

The clinical and demographic characteristics of the patients were determined by the Student t-test if the distribution of the continuous variables was normal, if not with the Mann-Whitney U test; categorical variables will be compared with chi-square test. Kappa and lambda levels, serum albumin levels, Kt / V, FGF-23, intracellular cytokine levels if the distribution is normal with Student's t-test and if not with the Mann-Whitney U test. In cases where more than two groups have flow cytometry, ANOVA and Tukey's post-hoc test will be compared with Student's t-test in two groups.

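### Residual kidney function is neither recorded nor accounted for, so native clearance dilutes the dialyser difference in serum middle-molecule levels and adds variance that the unpaired tests leave in

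*Combined protocol and SAP*

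**What the plan says.** The Study Group section sets two entry conditions. The first is age, given with the number of patients: "A total of 52 patients older than 18 years and under 65 years of age". The second is dialysis vintage, followed by the length of the study: "who have been undergoing hemodialysis for more than 3 months will be included in the study. The planned study time is 6 months". Vintage has no upper limit, and there is no exclusion list.

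Patients are randomised by computer, with no stratification factor named: "26 patients were dialyzed by high-flux dialyzer and 26 patients by middle cut-off dialyser for 3 months". They then switch: "At the end of the third month, the dialysers will be crossing in the same groups".

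The Clinical Evaluation section fixes the visits: "Serum samples will be taken at 0 (beginning), 4th (90th day) and 7th (180th day) months in the beginning and at the end of dialysis". It also states the comparison at issue: "Between the two groups, serum light chain kappa, serum light chain lambda and β 2 microglobulin and myoglobin levels will be compared". The only control on clearance is a urea Kt/V above 1.4, with no native component mentioned.

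The Statistical Analysis section tests kappa and lambda, among other variables, with Student's t-test or, if not normal, the Mann-Whitney U test. The Mann-Whitney alternative shows that the two-sample t-test is meant. No patient, period or sequence term and no covariate is named. Beta-2 microglobulin and myoglobin are not in that list and have no test of their own.

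Urine output and residual kidney function appear nowhere in the document.

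**The concern.** A steady-state serum level is generation divided by total clearance. Native kidney clearance, where a patient still has it, adds the same amount to the denominator on both dialysers, so the ratio of the two levels moves towards 1. An entry rule based only on more than 3 months of dialysis can mix patients who keep some native clearance with patients who have none.

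Two consequences follow for serum levels. The relative difference to be detected becomes smaller in patients with native function. The spread of levels between patients also becomes wider, and an unpaired test has to work against that spread. If the middle-molecule result is null, the trial will hold no data to tell similar membranes from a contrast blunted by native clearance. Urine volume that is not collected during the trial cannot be recovered afterwards.

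**Working it through.** **The plan's own figure.** The sample size of 52 (26 per group) comes without alpha, power, effect size or SD, so it cannot be reproduced. Back-calculated for an unpaired comparison at two-sided 0.05, the detectable standardised difference is (1.960 + 0.842) × √(2/26) = 2.802 × 0.2774 = 0.777 at 80% power.

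**Step 1: dilution for beta-2 microglobulin.** The inputs are all assumptions, none from the documents: 43 L/week cleared by high-flux, 52 to 58 L/week by middle cut-off and 30 L/week by non-renal routes. Native clearance is R = 10.08 L/week per mL/min (60 × 24 × 7 = 10,080 mL).

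Relative difference = 1 − (43 + 30 + R)/(K + 30 + R) = (K − 43)/(K + 30 + R), where K is the middle cut-off clearance. The share lost against an anuric patient is R/(K + 30 + R).

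| Native clearance | R (L/week) | Difference, K = 52 | Difference, K = 58 | Share lost |
|---|---|---|---|---|
| 0 mL/min | 0 | 9/82 = 11.0% | 15/88 = 17.0% | none |
| 2 mL/min | 20.16 | 9/102.16 = 8.8% | 15/108.16 = 13.9% | 19–20% |
| 5 mL/min | 50.4 | 9/132.4 = 6.8% | 15/138.4 = 10.8% | 36–38% |

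These are figures for a single patient, not trial averages.

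**Step 2: the same without solute-specific clearances.** Let m be middle cut-off over high-flux clearance and r be native over high-flux clearance, with no non-renal term. The fall in level is (m − 1)/(m + r). For m = 1.2 (assumed) it is 0.2/1.2 = 16.7% at r = 0, 0.2/1.7 = 11.8% at r = 0.5 and 0.2/2.2 = 9.1% at r = 1. For any m above 1 the fall shrinks as r grows. The direction therefore does not depend on the assumed values, only the size.

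**Step 3: effect on the unpaired test.** A simulated 26/26 crossover assumed m = 1.2, half the patients with no native function and a mean r of 0.5 over all patients. Those with function then average r = 1, which is about 43/10.08 = 4.3 mL/min on the clearances of step 1. Compared with no native function in anyone:

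- the between-group log difference moved from −0.180 to −0.147;
- the between-patient SD of log level rose from 0.292 to 0.511;
- power of the unpaired test at day 90 fell from 59% to 18%;
- power of a within-patient analysis stayed near 100%.

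A normal approximation, Φ(difference/(SD × 0.2774) − 1.96), separates the two causes:

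- no native function: 0.180/(0.292 × 0.2774) = 2.22, power about 60%;
- dilution only: 0.147/(0.292 × 0.2774) = 1.81, about 44%;
- dilution and wider SD: 0.147/(0.511 × 0.2774) = 1.04, about 18%.

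The larger part of the loss is between-patient variance, which a within-patient analysis removes.

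**Step 4: decline over time.** The same mix was run with no membrane effect (m = 1) and a 30% loss of native function per 3 months (assumed). Levels on an unchanged high-flux dialyser rose by 0.066 log units in 3 months (e^0.066 = 1.068, about 7%). Middle cut-off minus high-flux was +0.054 in the sequence starting on high-flux and −0.055 in the other. The average is (0.054 − 0.055)/2 = −0.0005, effectively zero. The between-group contrasts at each visit were also about zero, and type I error was about 5%.

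**The case against.** Several counter-arguments stand.

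- **Decline.** A reader might infer that falling native function over 6 months biases the dialyser comparison. It does not. The groups are randomised and share the decline at each visit, and it cancels in a balanced crossover estimate (step 4). It adds noise, and it would mislead only a before/after reading within one sequence, which the plan does not specify for these markers.
- **Imbalance.** A reader might also infer that an unequal split of patients with urine output would pass for a dialyser effect. Chance imbalance is already covered by the test's type I error. It also largely reverses when the same patients switch dialyser at month 3.
- **Size.** Every clearance is assumed. The loss of more than a third needs 5 mL/min, and at 2 mL/min it is about a fifth. Nothing in the document says how many enrolled patients keep native function.
- **Cause.** Most of the power loss in step 3 comes from the unpaired test, which is a fault of the analysis as much as of entry.
- **Population.** Open entry is legitimate. A smaller effect in patients with native function is the true effect for them, and restricting entry answers a narrower question.
- **Scope.** No primary endpoint is named. The point concerns serum levels only. A within-session reduction ratio from the pre- and post-dialysis samples would be little affected, but the plan does not name one as an endpoint.
- **Measurement.** Urine volume is only a proxy for native middle-molecule clearance.

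These limit the point to dilution, avoidable variance and an ambiguous null result. They do not remove it, because the plan neither records residual function nor uses an analysis that would take out its variance.

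**Conclusion.** The point holds as a worthwhile, inexpensive improvement, not as a flaw that invalidates the trial. Native clearance must shrink the relative dialyser difference in serum middle-molecule levels in any patient who has it. It also widens the between-patient spread, which the tests named in the Statistical Analysis section leave in the error term.

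For beta-2 microglobulin, on the assumed clearances, the loss is about a fifth at 2 mL/min, more than a third at 5 mL/min and zero in an anuric patient. The trial-average loss cannot be stated, because prevalence is not given. If nearly all patients are anuric it is small, but as planned the trial could not show that. The fall in power to 18% belongs to one assumed mix of patients and should not be read as the power of this trial.

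The documents do not support a claim of biased randomised comparison or inflated type I error, or a need to exclude patients who pass urine.

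**What to change.** 1. Record daily urine volume at baseline, day 90 and day 180, the three visits already planned.
2. Stratify the computer randomisation by baseline urine volume, at a cut-off that the sponsor specifies in advance. The documents give no basis for a particular value.
3. Analyse the middle-molecule levels within patient, with dialyser, period and sequence terms and urine volume as a covariate. Name beta-2 microglobulin and myoglobin in this analysis alongside kappa and lambda. The day 90 and day 180 volumes post-date randomisation, so also give the estimate without the covariate.
4. Report the dialyser difference by urine-volume stratum as a supportive analysis beside the overall result.
5. Keep entry open.

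The cost is one extra question per visit and one stratification factor, with no new procedure. With 52 patients the stratum results will be imprecise and should be presented that way. The within-patient analysis uses samples already planned.

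### Do the 4th- and 7th-month sampling labels put samples on the wrong dialyser or after the end of the study?

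*Combined protocol and SAP*

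**What the plan says.** The Study Group section sets out a two-period crossover in 52 patients: "26 patients were dialyzed by high-flux dialyzer and 26 patients by middle cut-off dialyser for 3 months". It then says "At the end of the third month, the dialysers will be crossing in the same groups" and "The study will end in three months after crossover". The overall length is given separately: "The planned study time is 6 months".

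The Clinical Evaluation section gives the serum schedule, with a month label and a day number for each on-treatment visit. After a first sample at time 0, the others come at "4th (90th day) and 7th (180th day) months in the beginning and at the end of dialysis". The next sentence, on the routine blood panel, repeats the month labels without the days: "Blood count, electrolytes, serum albumin and total protein levels will be determined at 0, 4th and 7th months".

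Neither section says whether the day-90 session is run before or after the dialyser is changed, or which dialyser is in use at the day-0 session.

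**The concern.** A period that ends after three months is normally sampled at month 3, and a six-month study has no month 7. Taken literally, the month labels put the first on-treatment visit in the second period and the last visit after the study.

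The question carries weight because blood is drawn at both ends of a session. A pre-dialysis value reflects the preceding weeks of treatment. A post-dialysis value also reflects the dialyser used that day. If the first on-treatment session were the first one on the new dialyser, the beginning sample would belong to the old device and the end sample to the new one. Within-session removal of light chains, β2 microglobulin and myoglobin could then be credited to the wrong dialyser in all 52 patients. The first period has only one on-treatment visit, so no other visit could correct the error. A similar question arises at day 0: if the assigned dialyser is already in use, the end-of-session sample is not a pre-treatment value.

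**Working it through.** **Inputs.** From Study Group: first period 3 months, switch at its end, second period 3 months, total 6 months. From Clinical Evaluation: sampling at days 0, 90 and 180, the last two labelled 4th and 7th month. The document does not define a month, so two lengths are assumed: 30 days and the average calendar month of 30.4375 days.

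**Stated days against the design.** Elapsed day = number of months × month length.

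| Month length | Switch (3 months) | Day 90 relative to switch | Study end (6 months) | Day 180 relative to end |
|---|---|---|---|---|
| 30 days | 3 × 30 = 90 | 0 | 6 × 30 = 180 | 0 |
| 30.4375 days | 3 × 30.4375 = 91.3 | 1.3 days before | 6 × 30.4375 = 182.6 | 2.6 days before |

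The day numbers reproduce the two period ends.

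**Labels read as elapsed months.** With 30-day months, month 4 is 4 × 30 = day 120, which is 30 days after the switch. Month 7 is 7 × 30 = day 210, which is 30 days after study end. At an assumed three sessions a week, 30 days is 30 / 7 × 3 ≈ 13 sessions on the other dialyser. This reading contradicts the day numbers in the same sentence.

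**Labels read as ordinals.** The 4th month runs from day 90 to day 120 and the 7th from day 180 to day 210. Their starting points are day 90 and day 180. Labels, days, switch and study end then all agree, at the boundary.

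**The panel without day numbers.** Its sentence directly follows the one that ties the same labels to days, so the days carry over.

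**What a post-switch session at day 90 would affect.** The pre-dialysis values would still reflect three months on the first dialyser. Only post-dialysis values and within-session quantities would change device. Clinical Evaluation speaks of comparing levels. Statistical Analysis also lists levels, together with Kt/V, and names no reduction ratio for the middle molecules. Day 180 has no later switch.

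**The case for a change.** The strongest reply is that the day numbers do not settle everything. Day 90 is itself the switch point, and no visit window is given. On an assumed three-sessions-a-week schedule, day 90 will often not be a dialysis day, so the nearest session could fall on either side of the change. Three calendar months span 89 to 92 days, so for some start dates day 90 comes a day after the calendar switch. Kt/V, usually computed from both ends of a session, would carry the dialyser in use that day. Blood drawn on the wrong device cannot be redrawn, and a sentence of clarification would cost nothing.

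The sequencing gap is real. But it leads to an error only if the session is run on the new dialyser, the result is then recorded under the old one, and the analysis uses post-dialysis or within-session values. The document calls for none of the first two steps. The visit closes a three-month treatment period, and a team running a crossover would sample before changing the device. If a session did fall just after the change, the treatment record would show which dialyser was used. The 30-day and 13-session figures further require staff to ignore days 90 and 180.

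The day-0 point is weaker. The text describes that visit only as the beginning and never calls its end-of-session sample a baseline. The beginning sample is a valid pre-treatment value whichever dialyser follows, and a post-dialysis sample on the assigned device could be an intended single-session measure. Requiring both samples before first use would be a preference.

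**Conclusion.** The concern does not call for a change. The month labels are awkward, but the days beside them match the switch and the study end: exactly with 30-day months, and within 1.3 and 2.6 days, on the early side, with average calendar months. Followed by those days, with the period-end sample taken before the device is changed, the schedule puts none of the 52 patients on the wrong dialyser at day 90 and takes no sample after the study has ended. Mislabelling all 52 patients and reversing the comparison is a worst case that the text does not prescribe.

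This rests on two assumptions: that sites follow the day numbers, and that they close a period before opening the next. Both are ordinary practice. The order of sampling and switching is a detail that investigators fill sensibly, and writing it down would not alter the design, the number of samples or the analysis.

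### The four-solute comparison names no draw, day or period, and the stated tests use neither the crossover pairing nor the day-0 value

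*Combined protocol and SAP*

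**What the plan says.** All references are to the combined protocol and SAP.

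- **Design (Study Group).** "26 patients were dialyzed by high-flux dialyzer and 26 patients by middle cut-off dialyser for 3 months". Then: "At the end of the third month, the dialysers will be crossing in the same groups".
- **Sampling (Clinical Evaluation).** Serum "samples will be taken at 0 (beginning), 4th (90th day) and 7th (180th day) months in the beginning and at the end of dialysis". That is six values per patient for each solute.
- **Comparison (Clinical Evaluation).** "Between the two groups, serum light chain kappa, serum light chain lambda and" beta-2 microglobulin and myoglobin are to be compared as levels. The sentence is complete, and it gives no draw, day, period, change score or reduction ratio.
- **Albumin, by contrast (Clinical Evaluation).** "The decrease in serum albumin values over time will be compared between the two groups". Here a time element is stated.
- **Test (Statistical Analysis).** "Kappa and lambda levels, serum albumin levels, Kt / V, FGF-23, intracellular cytokine levels" are assigned Student's t-test, or Mann-Whitney U if not normal. No pairing, period term or covariate appears. Beta-2 microglobulin and myoglobin are not in the list.

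**The concern.** Three things are left open or unused.

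1. **What is compared.** A start-of-session value is the patient's standing level. An end-of-session value is what remains after one treatment. They answer different questions.
2. **When it is compared.** Because the dialysers are exchanged, a difference between the randomised groups at day 90 and the same difference at day 180 estimate the dialyser effect with opposite signs. Leaving the day open therefore changes the meaning of the result, and it lets the reported comparison be picked after the data are seen.
3. **How it is compared.** Each patient is measured on both dialysers and also at day 0. The unpaired two-sample tests use neither fact, so information already being collected is discarded in a trial of 52 patients for which no sample-size rationale is given.

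**Working it through.** **Inputs from the documents:** 52 patients, 26 per group; two periods with exchange after month 3; samples on days 0, 90 and 180 at the start and end of the session; unpaired t or Mann-Whitney for kappa and lambda.

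**Assumed, because the documents give none of these:** two-sided 5%, 80% power, SD = 1, no dropout, the same correlation r between any two visits, no carryover, and the day-90 session taken as the last on the first dialyser. The plan has no power figure to reproduce.

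**Step 1. Unpaired first-period test, 26 v 26.** The standard error is √(2/26) = 0.277 SD. With 50 degrees of freedom, 80% power needs a difference of about 2.857 standard errors, so the detectable difference is 2.857 × 0.277 = 0.79 SD.

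**Step 2. Within-patient contrast, all 52, with a period term.** The variance is 2(1 − r)/52, which is (1 − r)/2 of the variance in step 1. The detectable difference is 0.792 × √((1 − r)/2). For r = 0.5 this is 0.792 × √0.25 = 0.40 SD.

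**Step 3. First-period ANCOVA on the matching day-0 value.** The variance relative to step 1 is (1 − r²)(1 + 1/48), where the second factor is the cost of estimating the slope. For r = 0.5 this is 0.75 × 1.021 = 0.766, and the detectable difference, on 49 degrees of freedom, is 0.69 SD.

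| Assumed r | Unpaired t | ANCOVA on day 0 | Within-patient |
|---|---|---|---|
| 0.3 | 0.79 SD | 0.76 SD | 0.47 SD |
| 0.5 | 0.79 SD | 0.69 SD | 0.40 SD |
| 0.7 | 0.79 SD | 0.57 SD | 0.31 SD |
| 0.8 | 0.79 SD | 0.48 SD | 0.25 SD |

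ANCOVA breaks even where (1 − r²)(49/48) = 1, so r² = 1/49 and r = 0.14. Below that it gains nothing. The within-patient contrast has no such threshold: even at r = 0 its variance is half that in step 1. In 20,000 simulated trials at each of r = 0, 0.3, 0.5, 0.7 and 0.8, the ANCOVA variance ratios were 1.02, 0.93, 0.77, 0.52 and 0.37, as the formula predicts.

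**Step 4. Open choice of comparison.** This is the chance, with no true difference, that at least one eligible comparison for a solute gives p < 0.05. It was simulated for 26 v 26; the correlation is that between the start and end draws and, where both days count, also between days.

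| Eligible comparisons | Correlations 0.9 | Correlations 0.3 | Independent (upper limit) |
|---|---|---|---|
| Day 90 only: start, end | 7.2% | 9.5% | 1 − 0.95² = 9.75% |
| Days 90 and 180: start, end | 9.7% | 17.6% | 1 − 0.95⁴ = 18.5% |

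The two rows belong to different readings of the plan. The ANCOVA gain in step 3 presupposes a first-period analysis, so the second row cannot be set beside it.

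**The case against.** **The stated tests are valid.** This stands. Randomisation makes an unadjusted day-90 comparison unbiased. A reader might infer that the missing day-0 covariate biases the result, but nothing in the documents supports that. The loss is precision.

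**No first-period analysis is planned, so a missing day-0 covariate may be beside the point.** This stands in large part. The documents describe a crossover, where the larger loss is the ignored pairing; ANCOVA is the second-best remedy. A first-period reading remains possible only because the stated tests are unpaired.

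**The gain depends on an r the documents do not give.** This also stands. At r = 0.3 ANCOVA takes 0.79 SD only to 0.76 SD. It would be too strong to say that omitting the covariate must cost precision. Repeat values in the same patient make r above 0.14 plausible, but that is an assumption.

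**The false-positive figures are a worst case.** They are. They suppose that only the most favourable result is reported, whereas the text is equally compatible with reporting every draw and day. A reader might also put the 10% to 18% range next to the ANCOVA gain as one combined cost. The documents do not support that, because the range needs day 180 to be eligible and the gain needs it excluded.

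**Choosing the draw is the sponsor's decision.** Agreed. Both draws are planned and neither has priority, so the request is only that one be named.

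None of these objections removes the omission itself: no draw or day for four solutes, no test for two of them, and no use of pairing or day 0 for the other two.

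**Conclusion.** The point holds as one of specification and efficiency, not of validity. The comparison of kappa, lambda, beta-2 microglobulin and myoglobin is undefined as to draw and day, in a design where the day decides which dialyser each group is using. Beta-2 microglobulin and myoglobin have no stated test.

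For precision, the pairing matters most. For r from 0.3 to 0.8 the detectable difference falls from 0.79 SD to between 0.47 and 0.25 SD with a within-patient analysis, and to between 0.76 and 0.48 SD with first-period ANCOVA. These sizes rest on assumed error rates, an assumed r and, for the within-patient figures, equal between-visit correlation and no carryover. The false-positive exposure per solute is about 7% to 9.5% if only day 90 is eligible, or about 10% to 18% if both days are, and only under selective reporting.

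The change should be made before the data are analysed. The omission of draw, day and test does not depend on any assumed value; only the size of the gain does.

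**What to change.** 1. For all four solutes, name one draw as the level outcome. The start-of-session value is one reasonable choice.
2. Name one analysis and apply it to all four, including beta-2 microglobulin and myoglobin. Preferably, estimate the dialyser effect within patient: day 90 against day 180 by dialyser in use, with a period term, on the log scale if skewed.
3. If only the first period is to be used, replace the t or Mann-Whitney test with ANCOVA of the day-90 value on the day-0 value from the same draw, reported with a 95% CI. Do not claim this gain on top of the within-patient one.

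The cost is analysis wording only, on samples already planned. The within-patient analysis adds the assumption that the first dialyser's effect does not carry over to the day-180 sample, which is taken 90 days after the day-90 one. The plan should state that assumption.

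### The albumin comparison names no interval, and day 0 to day 180 by randomised group, which the text permits, is not a clean dialyser contrast

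*Combined protocol and SAP*

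**What the plan says.** All the relevant text is in three sections of the combined protocol and SAP.

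- **Study Group.** "Patients will be randomized in two groups by a computer program". In the first period, "26 patients were dialyzed by high-flux dialyzer and 26 patients by middle cut-off dialyser for 3 months". Then "At the end of the third month, the dialysers will be crossing in the same groups", and the study ends three months later. No washout is mentioned.
- **Clinical Evaluation.** "Blood count, electrolytes, serum albumin and total protein levels will be determined at 0, 4th and 7th months". Serum is drawn at 0, "4th (90th day) and 7th (180th day) months in the beginning and at the end of dialysis". The albumin comparison is a single sentence: "The decrease in serum albumin values over time will be compared between the two groups". It names neither an interval nor which of the two samples per session is used.
- **Statistical Analysis.** Albumin appears only in a list, "Kappa and lambda levels, serum albumin levels, Kt / V, FGF-23, intracellular cytokine levels if the distribution is normal", to be compared by Student's "t-test and if not with the Mann-Whitney U test". This section speaks of levels and not of a decrease. It has no time point, baseline adjustment, within-patient comparison or period term.

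**The concern.** Three visits give three possible intervals: days 0-90, 90-180 and 0-180. The only groups that the document defines are the randomised ones, so the comparison is most naturally by randomised group. If 'over time' is then taken as the whole study, the result is day 0-180 change by randomised group. At day 180 both groups have had three months on each dialyser and differ only in the order.

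An analyst following the text could therefore report little or no albumin difference because part of the first-period loss persists after the switch, even if the dialysers do differ. Because the interval is open, it could also be chosen once the data are known. More albumin loss on one dialyser would be an unwanted effect, so a falsely reassuring comparison matters.

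**Working it through.** The documents give no alpha, effect size, SD or power, so there is no figure of the plan's own to reproduce. The algebra below needs no outside number; the illustration does.

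**Inputs from the documents.** 26 patients per group; visits at days 0, 90 and 180; exchange of dialysers at the end of month 3.

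**Assumed.** d is the extra fall in albumin after three months on middle cut-off compared with high-flux. c is the share of the first-period effect still present at day 180, from 0 to 1. Baselines are equal in expectation by randomisation, and a common period change cancels between groups.

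**Step 1: expected change from day 0, relative to high-flux with no common trend.**

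| Group | Day 90 | Day 180 |
|---|---|---|
| Middle cut-off first | -d | -cd |
| High-flux first | 0 | -d |

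**Step 2: contrasts.**

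- Day 0-90, middle cut-off first minus high-flux first: -d - 0 = -d, for any c.
- Day 0-180, same order: -cd - (-d) = +(1-c)d. This is full size at c = 0, half at c = 0.5 and zero at c = 1. The sign is reversed because the greater fall belongs to the group on middle cut-off at day 180, the one that started on high-flux.
- Within patient, middle cut-off minus high-flux, averaged over the two sequences: [-(1-c)d + (-d)]/2 = -(1-c/2)d. A common period change enters the two sequences with opposite signs and cancels.

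**Step 3: illustration.** Assumed: d = 0.20 g/dL, SD 0.35 at each visit, correlation 0.7 between any two visits, two-sided 5% level.

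- SD of a change: 0.35 × √(2 × 0.3) = 0.271. Standard error of the group difference: 0.271 × √(2/26) = 0.075.
- ANCOVA residual SD: 0.35 × √(1 - 0.49) = 0.250. Standard error: 0.250 × √(2/26) = 0.069.
- Within-patient standard error: 0.075/2 = 0.038.

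Simulation of 20,000 trials per scenario gave these rates of significance:

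| Analysis | c = 0 | c = 0.5 | c = 1 |
|---|---|---|---|
| Day 0-180 change by randomised group (t-test) | 74% | 26% | 5% |
| Day 0-90 change by randomised group (t-test) | 74% | 74% | 74% |
| Day 0-90 ANCOVA | 80% | about 80% | 80% |
| Within patient, with period | 99.9% | 97% | 74% |

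The size of the day 0-180 contrast is 0.20, 0.10 and 0.00. The within-patient estimate is -0.20, -0.15 and -0.10.

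**Step 4: range.**

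- If correlation decays to 0.49 over 180 days, the day 0-180 row becomes 51%, 17% and 5%. The ANCOVA and within-patient rows are essentially unchanged.
- Over SD 0.30 to 0.45, adjacent-visit correlation 0.5 to 0.8 and both correlation patterns, day 0-180 gives 24-96% at c = 0 and 10-46% at c = 0.5. Day 0-90 ANCOVA gives 43-98%. The within-patient analysis gives 65-100% at c = 0.5 and 35-96% at c = 1.

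**The case against.** **The harm is conditional.** Attenuation needs c above 0, and the documents say nothing about c. At c = 0 with equal correlation, day 0-180 has the same power as the like-for-like day 0-90 t-test, 74% each. This stands. The step from 74% to 80% is the gain from baseline adjustment and should not be counted against the choice of interval.

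**'Over time' may mean all three visits.** The valid day 0-90 contrast would then be reported beside day 0-180. That is plausible, but the text does not say so, does not say which contrast would count, and names only two-sample tests.

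**A sensible analyst would choose day 0-90.** Perhaps, but nothing in the plan requires it.

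Three stronger readings are tempting and are not supported:

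- A reader might infer that it is wholly unclear whether the groups are the randomised groups or the dialyser in use. The text leans clearly to the randomised groups: they are the only ones defined, and the exchange takes place within them.
- A reader might infer that both periods will be pooled by current dialyser in a two-sample test, counting each patient twice. No section proposes that test, so its error rate is not a defect of this plan.
- A reader might infer that the fall will be credited to the wrong dialyser. That takes a further mistake, labelling a day-180 result by starting dialyser despite a documented exchange. The plan does not prescribe it.

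**Conclusion.** The point holds in a limited form and should be fixed. The interval for the albumin comparison is not stated. One permitted reading, day 0-180 by randomised group, returns only (1-c) of the dialyser effect and reflects the dialyser in use at day 180; another, day 0-90 by randomised group, is valid. The factor (1-c) follows from the design, given that c lies between 0 and 1. The fall in power from 74% to 26% at c = 0.5, and to the 5% error rate at c = 1, rests on assumed values of d, SD, correlation and c, none of them measured in this trial. The documents do not show that the albumin result will be wrong. They leave open a comparison that could hide a real difference. The point is confined to albumin, the only marker that Clinical Evaluation compares as a change.

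**What to change.** **In Clinical Evaluation, replace the albumin sentence with wording to this effect:**

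> Change in albumin from day 0 to day 90 will be compared between the randomised groups by ANCOVA adjusted for day-0 albumin. The day-90 sample will be taken before the dialyser switch, and the same sample (beginning or end of dialysis, to be named here) will be used at every visit. Day-90 and day-180 albumin will also be compared between dialysers within patient, with period in the model; carry-over from the first period would attenuate this estimate. Day 0 to day 180 change by randomised group will not be used as evidence about the dialyser.

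The timing line is needed because the second visit is labelled both day 90 and 4th month, while the switch is at the end of month 3.

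**In Statistical Analysis, amend to match.** Otherwise the two sections would conflict. Remove albumin from the Student's t / Mann-Whitney list, name the two analyses, and give a fallback for non-normal data. Examples are rank-based ANCOVA and a Mann-Whitney test between sequences on the within-patient period differences. State before the data are seen which analysis is the main one; that choice is the sponsor's.

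**Cost.** Only wording and one timing rule change; all samples are already planned. Naming day 0-90 by randomised group with the existing t-test would cure the core defect, and ANCOVA adds power (about 80% against 74% in the illustration). Neither analysis is free of drawbacks. Day 0-90 gives up within-patient precision (about 80% against 97% at c = 0.5). The within-patient estimate shrinks with carry-over, to half the true effect at c = 1. In the illustration the within-patient analysis has the higher power up to about c = 0.9 (82% against 80%) and the lower at c = 1 (74%).
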